To assess the hypothesis that higher mutational load is associated with pCR rate, the study will assess the association between overall mutational load and pCR rate. We will first calculate the per megabase mutation rate for each individual. Then we will use logistic regression to regress pCR status on the mutation rates and use a 1-degree freedom likelihood ratio test to obtain a p-value for the association between response and mutation rate. We will control the type I error at the two-sided alpha=0.05 level. We estimated the minimal detectable odds-ratio under the assumption that we will collect exome sequencing data on 25 patients and that we will control the type I error rate at the two-sided alpha=0.05 level. In prior data, the median number of mutations per megabase in desmoplastic melanoma was found to be 62 and the 25th and 75th percentiles were 33 and 101, respectively (private communication, [name] to [name], 11/18/2014). Therefore, by matching the quantiles, we approximate the distribution of the per megabase mutation rate across patients as a Weibull with shape parameter 1.4 and scale parameter 80. Assuming a baseline response rate of 5%, we anticipate over 80% power to detect a log odds-ratio of 0.31 (corresponding to an odds-ratio of 1.36) for each 10 mutation increase in the per megabase mutation rate. If logistic regression is unstable or behaves poorly, e.g. due to low response rates, we will also consider robust and flexible alternatives such as the Wilcoxon test to compare mutation rates between responders and nonresponders.

The study will examine whether change in T-cell infiltration following treatment is higher in the DM patients who respond. Specifically, we will compute the change in CD8 expression from baseline to resection and then compare the change between responders and non-responders using a two-sample t-test. We will control type I error at the alpha=0.05 level. Assuming that 25% of patients respond, then we anticipate 80% power to detect a difference in mean CD8 expression change 1.35 standard deviations. We will repeat the analysis comparing the change in CD8 expression from baseline to week 4 to determine whether T-cell infiltration in the on-treatment biopsy is associated with response at resection.

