To assess the hypothesis that higher mutational load is associated with CR rate, the study will assess the association between overall mutational load and CR rate. We will first calculate the per megabase mutation rate for each individual. Then we will use logistic regression to regress CR status on the mutation rates and use a 1-degree freedom likelihood ratio test to obtain a p-value for the association between response and mutation rate. We will control the type I error at the twosided alpha=0.05 level. We estimated the minimal detectable odds-ratio under the assumption that we will collect exome sequencing data on 21 patients and that we will control the type I error rate at the two-sided alpha=0.05 level. In prior data, the median number of mutations per megabase in desmoplastic melanoma was found to be 62 and the 25th and 75th percentiles were 33 and 101, respectively (private communication, [name] to [name], 11/18/2014). Therefore, by matching the quantiles, we approximate the distribution of the per megabase mutation rate across patients as a Weibull with shape parameter 1.4 and scale parameter 80. Assuming a baseline response rate of 5% we anticipate over 70% power to detect a log odds-ratio of 0.45 (corresponding to an odds-ratio of 1.57) for each 10 mutation increase in the per megabase mutation rate. If logistic regression is unstable or behaves poorly, e.g. due to low response rates, we will also consider robust and flexible alternatives such as the Wilcoxon test to compare mutation rates between responders and non-responders.

The study will examine whether change in T-cell infiltration following treatment is higher in the DM patients who respond. Specifically, we will compute the change in CD8 expression from baseline to progression and then compare the change between responders and non-responders using a two-sample t-test. We will control type I error at the alpha=0.05 level. Assuming that 20% of patients respond, then we anticipate 80% power to detect a difference in mean CD8 expression change 1.61 standard deviations. We will repeat the analysis comparing the change in CD8 expression from baseline to week 4 to determine whether T-cell infiltration in the on-treatment biopsy is associated with response at progression.

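### Cohort B's minimal detectable odds ratio for mutational load (1.57 at over 70% power) does not follow from the stated inputs and does not fit the Cohort A figure

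*Combined protocol and SAP*

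**What the plan says.** Section 11.2d plans a logistic regression of complete response on the per-megabase mutation rate and will "use a 1-degree freedom likelihood ratio test to obtain a p-value for the association between response and mutation rate". The power statement is made "under the assumption that we will collect exome sequencing data on 21 patients" and on the basis that "we will control the type I error rate at the two-sided alpha=0.05 level". The mutation rate is modelled "as a Weibull with shape parameter 1.4 and scale parameter 80", chosen to match prior data in which the median "was found to be 62 and the 25th and 75th percentiles were 33 and 101, respectively". With the baseline response rate set at 5%, the result reads "we anticipate over 70% power to detect a log odds-ratio of 0.45" (odds ratio 1.57) per 10 mutations/Mb. The paragraph introduces this as an estimate of the minimal detectable odds ratio.

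Section 11.1d has the same paragraph for Cohort A, with pathologic complete response as the endpoint and 25 patients: "we anticipate over 80% power to detect a log odds-ratio of 0.31" (odds ratio 1.36). Section 11.2d says the Cohort B translational analyses match Cohort A's apart from the endpoint. Neither section says whether the 5% is the response rate at zero mutations, at a typical load, or overall.

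**The concern.** As far as the text shows, only the sample size differs between the two calculations. Four fewer patients are said to raise the smallest detectable log odds ratio from 0.31 to 0.45, which is 45% larger (0.45/0.31 = 1.45), and to lower the power as well. A rough scaling suggests this is too much. With information proportional to n, 0.31 becomes 0.31 × √(25/21) = 0.34 at unchanged power. Moving from 80% to 70% power multiplies that by (1.96 + 0.52)/(1.96 + 0.84) = 0.89, giving about 0.30.

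At stake is how informative Cohort B is taken to be for objective 1.3a, the hypothesis behind the trial's rationale. No sample size or decision rule depends on the figure.

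**Working it through.** **Inputs** (sections 11.1d and 11.2d): n = 21 and β = 0.45 for Cohort B; n = 25 and β = 0.31 for Cohort A; X = mutations per Mb divided by 10; 1-df likelihood ratio test at two-sided 0.05 (critical value 3.841); Weibull(1.4, 80); 5% baseline.

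**What reproduces.** exp(0.45) = 1.57 and exp(0.31) = 1.36, as stated. The Weibull quartiles are 32.9, 61.6 and 101.0, against 33, 62 and 101 in the plan. Its mean is 72.9.

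**Model.** logit P(response) = a + βX. The undefined baseline enters through a:
- 5% at zero mutations: a = ln(0.05/0.95) = −2.94.
- 5% at median load: a = −2.94 − 6.16β, which is −5.72 for β = 0.45.
- 5% at mean load: a = −2.94 − 7.29β, which is −6.22 for β = 0.45.
- 5% overall: a is solved so that the average response over the Weibull is 5%.

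**Power.** Simulated with the plan's likelihood ratio test, 20,000 datasets per setting. A dataset with no responder counts as no detection; a separated dataset is judged on its likelihood ratio. Independent runs agree to within about 2 points. The last row is not a 5% reading and is shown for comparison.

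| Where the rate applies | Cohort B (n = 21, 0.45) | Cohort A (n = 25, 0.31) |
|---|---|---|
| 5% at zero mutations | 95% | 88% |
| 5% at median load | 89% | 76% |
| 5% at mean load | 86% | 71% |
| 5% overall | 55% | 49% |
| Overall rate at the design value (20% / 25%) | 91% | 85% |
| *Plan* | *over 70%* | *over 80%* |

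No row gives Cohort B about 70%, and B exceeds A in every row. Placing the 5% at the 25th percentile of load gives the same ordering (95% against about 84%). An overall rate of about 8% would be needed to bring Cohort B to 70%.

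**Is 0.45 minimal?** Of the four 5% readings in the table, only zero mutations supports Cohort A's claim. On that reading, n = 21 gives:
- about 70% power at log odds ratio 0.25 to 0.26 (odds ratio about 1.29);
- about 80% at 0.30 (odds ratio 1.35);
- about 82% to 83% at Cohort A's own 0.31.

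So 0.45 is well above the minimum. That reading has its own difficulty: at β = 0.45 it implies an overall complete response rate of about 50%, whereas the other responder comparisons in 11.2d assume 20%.

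**If 5% is the overall rate,** 55% and 49% both fall short of the stated powers, and about a third of simulated Cohort B datasets contain no responder.

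**The case against.** Four points have force.

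1. The plan says over 70%, which is a lower bound, and 95% satisfies it literally. That stands as a reading of the power alone. It does not rescue the description of 1.57 as the minimal detectable odds ratio.

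2. A reader might infer that Cohort B really has 95% power, so that the plan understates it by roughly 25 points. The documents do not support that. The figure belongs to one reading of an undefined term, the range is 55% to 95%, and with 5% overall the plan overstates power. For the same reason, it is not established that a null Cohort B result would be wrongly dismissed as inconclusive.

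3. A reader might also infer that no sensible calculation could give the stated pair. That is too strong. Separation is common at n = 21, and 11.2d itself allows for unstable logistic fits. If separated fits are not counted as detections, overall rates of 20% and 25% give about 69% for B and 82% for A, close to both claims. But the plan states no such rule and names 5%, not those rates. A Wald test with 5% at zero mutations gives B about 68% to 69% and A about 75%; it reaches neither stated power and is not the specified test.

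4. The likelihood ratio test is somewhat liberal at n = 21, with simulated type I error about 7%. Holding it at 5% lowers Cohort B power at 0.45 only to about 93% (5% at zero mutations) or 87% (overall 20%).

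**Conclusion.** The Cohort B power statement does not follow from the inputs given, and it is inconsistent with the Cohort A statement. The ordering result does not depend on the meaning of the baseline: with the plan's own test, B at 0.45 has more power than A at 0.31 on every reading tried. The size of the error does depend on it. If 5% is the rate at zero mutations, power is about 95% and the minimal odds ratio is nearer 1.29 (70% power) or 1.35 (80%) than 1.57. If 5% is the overall rate, both cohorts' stated powers are too high, at 55% and 49%. Whether the cause is a slip or an undocumented simulation rule cannot be told from the documents.

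These results assume the Weibull in the plan, complete exome data on all 21 and 25 patients, and the uncalibrated likelihood ratio test. The consequence is small: objective 1.3a is listed under other objectives, Cohort B is a pilot, and neither primary design uses the figure.

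**What to change.** In 11.1d and 11.2d, state where the 5% baseline applies and how separated and no-responder datasets are counted. Recompute both cohorts by that one method and restate the Cohort B figure. With the plan's uncalibrated likelihood ratio test and the counting rule used above, it would read:
- 5% at zero mutations: about 80% power at log odds ratio 0.30 (odds ratio 1.35) per 10 mutations/Mb; or
- overall complete response 20%, as in the other Cohort B comparisons: about 80% power at log odds ratio 0.33 to 0.34 (odds ratio about 1.40).

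If 5% is meant as the overall rate, lower the stated power in both sections. The cost is a short simulation and a sentence or two in each section, with no change to sample size, data collection or analysis.

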11.2 Cohort B

a. As a pilot study, Cohort B will use a single stage design with an accrual goal of 21 eligible patients. The anticipated accrual rate for Cohort B is 1 patient per month. Assuming an ineligibility rate of 20%, the study will accrue 26 total patients to enroll 21 eligible patients.

b. Primary Endpoint

The primary endpoint for Cohort B is complete response rate (CR). Given that Cohort B is intended as a pilot trial, we propose single stage design with the assumption that a true CR of 20% or higher indicates that the treatment is of considerable interest for patients with unresectable/metastatic DM whereas a true CR of 5% or lower indicates that the treatment will not be of further interest. Specifically, we will enroll 21 eligible patients with unresectable/metastatic DM. Three or more complete responses out of 21 would be considered evidence that the treatment warrants further study, provided other factors such as toxicity and overall survival also appear favorable. This design has an alpha of 8.5% (i.e. probability of declaring the regimen warrants further study when the true CR is 5%) and a power of 82% (probability of declaring the regimen warrants further study when the true CR is 20%). The higher alpha and lower power used in this design reflect the intention to use this as a pilot trial.

Secondary Endpoints

For the secondary endpoints, 21 eligible patients will be sufficient to estimate the PFS and OS at a particular time point (e.g. 9 weeks) to within ±21.4% (95% confidence interval). However, since PFS is estimated only among patients who do not undergo resection, we will only be able to estimate the PFS to within ±21.9%, ±22.5%, or ±23.9% (95% confidence intervals) if the percentage of patients who undergo resection is 5%, 10%, or 20%, respectively.

d. Translational Medicine Objectives: The statistical analysis of the translational medicine objectives for Cohort B will be the same as for Cohort A except we will use CR as the endpoint instead of pCR.

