To assess the hypothesis that ctDNA fraction at baseline and week 4 are associated with response in DM patients, we will assess the association between response and ctDNA fraction using a two-sample t-test at the two-sided $\alpha = 0.05$ level. Assuming that 20% of patients respond, then we anticipate 80% power to detect a difference in mean ctDNA fraction of 1.61 standard deviations.

To assess the hypothesis that TCR clonality is higher in DM patients who respond, suggesting that the T-cells are targeting the tumor, we will compute the clonality metric as the normalized Shannon entropy for all patients at baseline, Week 4, and progression. We will then compute the change in clonality metric from baseline to progression. The change in clonality will be compared between responders and non-responders using a two-sample t-test with significance determined at the two-sided alpha=0.05 level. Assuming that 20% of patients respond, then we anticipate 80% power to detect a difference in clonality change of 1.61 standard deviations. We will repeat the analysis comparing the change in clonality from baseline to Week 4 to determine whether T-cell clonality in the on-treatment biopsy is associated with response at progression.

The study will examine adaptive immune resistance by first evaluating whether PD-L1 expression is increased at Week 4 and progression as compared to baseline using paired t-tests and controlling the type I error at the two-sided alpha=0.05 level. With 21 patients, we anticipate 80% power at each time point to detect a mean difference in expression of 0.64 standard deviations. We will further evaluate whether increased PD-L1 expression at Week 4 or at progression is

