associated with response. Specifically, we will compute the change in expression from baseline to progression and then compare the change between responders and non-responders using a two-sample t-test. We will control type I error at the two-sided alpha=0.05 level. Assuming that 20% of patients respond, then at each time point we anticipate 80% power to detect a difference in mean PD-L1 expression change of 1.61 standard deviations. We will repeat the analysis comparing the change in PD-L1 expression from baseline to Week 4 to determine whether T-cell infiltration in the on-treatment biopsy is associated with response at progression. In addition to our assessment of overall mutational load, we will further conduct a neoantigen analysis. Specifically, we will predict the immunogenicity of each nonsynonymous somatic mutation using NetMHC. We will then use logistic regression to regress CR status on the number of predicted immunogenic mutations, computing a p-value using a 1-df test and controlling type I error at the two-sided alpha=0.05 level.

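### Cohort B: the CD8, TCR clonality and PD-L1 comparisons of CR with non-CR rely on progression tissue that is optional and that a non-progressing CR never has, so the stated 80% power is not supported by the specimen schedule

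*Combined protocol and SAP*

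**What the plan says.** Section 11.2d carries the Cohort A translational analyses over to Cohort B with one change of endpoint: "we will use CR as the endpoint instead of pCR". The later tissue sample also changes, from resection to progression.

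- **CD8:** "we will compute the change in CD8 expression from baseline to progression and then compare the change between responders and non-responders". Power: "Assuming that 20% of patients respond, then we anticipate 80% power to detect a difference in mean CD8 expression change 1.61 standard deviations".
- **TCR clonality:** the metric is the "normalized Shannon entropy for all patients at baseline, Week 4, and progression", and then "We will then compute the change in clonality metric from baseline to progression". The 20% response rate, 80% power and 1.61 SD are repeated.
- **PD-L1, paired test of change over time:** "With 21 patients, we anticipate 80% power at each time point to detect a mean difference in expression of 0.64 standard deviations". Progression is one of the two time points.
- **PD-L1 by response:** "we will compute the change in expression from baseline to progression and then compare the change between responders and non-responders using a two-sample t-test", again with 80% power at 1.61 SD.
- **Week 4 repeat:** for CD8, "We will repeat the analysis comparing the change in CD8 expression from baseline to week 4". The same repeat is specified for TCR clonality and PD-L1.

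The specimen schedule is elsewhere. Section 15.1b and the tissue row of Calendar 9.2 list progression tissue as optional. Section 15.1b requires the biopsy at 3 to 5 weeks only if residual disease is left to sample, and surgical tissue only if a resection is done. Section 18.1 names baseline, 4-week and 9-week tissue for these assays and no progression sample.

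**The concern.** Whether the later measurement exists depends on the outcome being compared. Section 10.2 defines CR as disappearance of all target and non-target lesions (with a size rule for nodes). A CR that lasts through the 5-year follow-up in Section 7.9 produces no progression specimen. The CRs who can enter the test are those whose response later failed and who accepted an optional biopsy. The contrast labelled responder versus non-responder then compares relapsed CRs with progressing non-CRs, and it cannot be computed if no CR supplies tissue. Non-CR patients who do not progress, or who decline the biopsy, are lost as well. The plan gives no rule for missing progression tissue and no reduced sample size.

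Cohort A does not share the problem. Its later sample is the resection specimen, and Section 7.2 requires surgery for potentially resectable disease even after a RECIST complete response.

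At stake is the interpretation of the Cohort B biomarker comparisons. They are listed under other objectives in Section 1.3, yet they are planned as formal 5% tests with stated power.

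**Working it through.** **Inputs.** From Section 11.2d: n = 21, CR rate 20%, standardised difference 1.61 SD (two-sample), 0.64 SD (paired PD-L1), alpha 0.05. The CD8 sentence does not give sidedness; the TCR and PD-L1 text says two-sided, which is used here. The counts with tissue are my assumptions.

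**Formulas.** Two-sample t-test: df = n1 + n2 − 2, noncentrality λ = d·√[n1·n2/(n1 + n2)], power = P(|T| > t(0.975, df)) with T noncentral t. Paired test: df = n − 1, λ = d·√n.

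**Step 1: reproduce the plan.** All 21 patients at 20% CR gives 21 × 0.20 = 4.2 CR and 16.8 non-CR.

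- λ = 1.61 × √(4.2 × 16.8/21) = 1.61 × 1.833 = 2.951; df = 19; critical t = 2.093; power = 79.9%. The difference detectable at 80% power is 1.611 SD. A one-sided test would have given 1.41 SD.
- Paired PD-L1: λ = 0.64 × √21 = 2.933; df = 20; critical t = 2.086; power = 79.7%.

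The arithmetic in the plan is correct. What it takes for granted is a later sample from every patient. For TCR clonality this is stated outright. For the paired PD-L1 test it is implied by the 21 patients named at each time point. For CD8 and the PD-L1 responder test it is inferred from the reproduction above.

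**Step 2: reduce the number with progression tissue (1.61 SD).**

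| CR v non-CR with tissue (assumed) | λ | Power |
|---|---|---|
| 4 v 17 | 2.897 | 78% |
| 4 v 12 | 2.789 | 74% |
| 3 v 17 | 2.571 | 68% |
| 3 v 12 | 2.494 | 64% |
| 2 v 17 | 2.154 | 53% |
| 2 v 12 | 2.108 | 49% |
| 2 v 8 | 2.037 | 43% |
| 1 v 17 | 1.565 | 31% |
| 0 v any | – | no test |

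The difference detectable at 80% power rises from 1.61 SD to 1.96 SD (3 v 12) and 2.53 SD (2 v 8).

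**Step 3: chance of an empty responder group.** Let q be the assumed share of CRs who supply progression tissue. The number of CR specimens is Binomial(21, 0.20·q), and P(none) = (1 − 0.20·q)^21.

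- q = 0.75: mean 3.15, P(none) = 0.85^21 = 3%
- q = 0.50: mean 2.10, P(none) = 0.90^21 = 11%
- q = 0.25: mean 1.05, P(none) = 0.95^21 = 34%

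**Step 4: paired PD-L1 at progression (0.64 SD).** 21 pairs 80%; 15 pairs (λ = 2.479) 64%; 10 pairs (λ = 2.024) 44%.

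**Step 5: tissue time points for Cohort B.**

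| Place | Later tissue |
|---|---|
| Section 11.2d | Week 4 and progression |
| Section 15.1b | 3–5 weeks (if residual disease), surgery (if done), progression (optional) |
| Calendar 9.2 | Cycle 2 (Week 4), post-progression (optional) |
| Section 18.1 | Weeks 4 and 9, or Week 9 biopsy/resection for PD-L1; no progression |

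No Week 9 tissue is scheduled for Cohort B. The 9-week biopsy in footnote s belongs to the Cohort A calendar.

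**The case against.** The strongest case against acting is that the stakes are low. These are exploratory aims in a cohort labelled a pilot, no decision rule uses them, and the Week 4 comparison is already planned. A report would presumably show how many specimens were analysed. All of that stands and limits the weight of the point. It does not repair a contrast whose responder group is selected by relapse, or a power figure that ignores the specimen schedule.

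Four stronger readings are tempting, and the documents do not support them.

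- *The two-sample tests reach 80% only if all 21 patients supply tissue.* At 5 v 12, with 17 specimens, power is 81%. That needs more CRs than the 4.2 expected, but at a true 20% rate the chance of 5 or more CRs among 21 is 41%. The need for all 21 holds for the fixed 20% split and for the paired test.
- *Section 11.2d as a whole states that every patient has progression tissue.* The explicit wording covers TCR clonality only.
- *No CR can ever contribute.* CR includes unconfirmed CR (Sections 1.1 and 10.3), and follow-up runs to 5 years, so some CRs may relapse and be biopsied. They are a selected subset.
- *Every analysis of progression tissue is invalid.* The paired PD-L1 test asks whether expression rises at progression and does not compare CR with non-CR. It remains a coherent question among patients who progress, and it serves the adaptive-resistance objective.

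The Week 4 biopsy is not free of the problem either: an early complete responder with nothing left to biopsy is missing there too. If one of 4 CRs is missing, 3 v 17 gives 68%.

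**Conclusion.** The point holds for the Cohort B comparisons of CR with non-CR on the baseline-to-progression change. As written they are outcome-selected or, with no CR specimen, not computable. The stated 80% at 1.61 SD corresponds to complete tissue at the planned 20% CR rate. The schedule mismatch and the reproduced figures are firm. The size of the loss is not: the documents give neither a relapse rate among CRs nor an uptake for the optional biopsy, so 68% down to 43% illustrates plausible counts and is not an estimate. The paired PD-L1 test is affected only through its number of pairs. The Cohort B CR decision rule and the secondary endpoints are untouched. This should be corrected, but it does not threaten the trial's main conclusions.

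**What to change.** 1. In Section 11.2d, make the already planned baseline-to-Week-4 change the main CR v non-CR comparison for CD8, TCR clonality and PD-L1, in patients with both samples. State that this biopsy is required only with residual disease, so outcome-dependent missingness is reduced and not removed.
2. Report the baseline-to-progression CR v non-CR contrasts descriptively, with the number of evaluable pairs by response.
3. Keep the paired PD-L1 test at progression. Describe it as applying to patients who progress and supply tissue, and give its power by evaluable pairs as in Step 4.
4. Replace the 80% progression statements for the two-sample tests with power by evaluable pairs, labelling the counts as assumptions and allowing for losses in both groups.
5. Reconcile the Cohort B tissue time points in Sections 9.2, 11.2d, 15.1b and 18.1. Say whether surgical specimens from resected Cohort B patients enter these analyses; Section 11.2 itself considers 5% to 20% undergoing resection.

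Leave the Cohort A analyses in Section 11.1d unchanged.

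**Cost.** Wording changes only, with no new specimens. The progression contrasts between CR and non-CR lose their status as formal tests.
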